8.1.1.5 WEEK 2 VISIT

At this visit, a medication reconciliation will be done, as well as documentation and review of adverse events. The first 6 subjects who had PK samples done at Day 0 will also have PK blood samples obtained before and 2 hours after dosing of study drug. A window of +/- 10 minutes will be given around each post-infusion draw time point. ECG should be done prior to infusion and two hours post-infusion (+/- 10 minutes). The following laboratory tests will be done prior to drug dosing: CMP, CBC, urinalysis, HIV VL, CD4, PT/INR, lipid panel, urine hCG (for females of child-bearing potential), and research immunology and inflammation labs. A dose of CD24Fc, 240mg vs placebo, will be infused intravenously, pending no laboratory abnormalities or adverse events which warrant holding the study drug. He/she must be fasting prior to blood draw.

8.1.1.6 WEEK 4 VISIT

At this visit, there will be a medication reconciliation and documentation and review of adverse events. The first 6 subjects who had PK samples done at Day 0 and Week 2 will also have PK blood samples obtained before and 2 hours after dosing of study drug. A window of +/- 10 minutes will be given around each post-infusion draw time point. ECG should be done prior to infusion and two hours post- infusion (+/- 10 minutes). The following laboratory tests will be done prior to drug dosing: CBC, urinalysis, HIV VL, CD4, PT/INR, lipid panel, urine hCG (for females of child-bearing potential), and research immunology and inflammation labs. A dose of CD24Fc, 240mg vs placebo, will be infused intravenously, pending no laboratory abnormalities or adverse events which warrant holding the study drug. He/she must be fasting prior to blood draw.

8.1.1.7 WEEK 6 VISIT

At this visit, there will be vital signs, a medication reconciliation and documentation and review of adverse events. The first 6 subjects who had PK samples done at Day 0, Week 2, and Week 4 will also have PK blood samples obtained. The following laboratory tests will be done prior to drug dosing: CMP,

CBC, urinalysis, HIV VL, CD4, PT/INR, lipid panel, urine hCG (for females of child-bearing potential), HbA1c, immunology labs, IL-6, apoB, Lp(a), urine albumin:creatinine ratio, Hs-CRP. Subjects participating in the FDG-PET/CT will also have GlycA, CEC, and NMR lipoprotein collected. He/she must be fasting prior to blood draw.

8.1.1.8 WEEK 16 VISIT

At this visit, vital signs, H&P and medication reconciliation will be done, as well as documentation and review of adverse events. The first 6 subjects who had PK samples done at Day 0, Week 2, Week 4, Week 6 will also have PK blood samples obtained. The following laboratory tests will be done: CMP, CBC, urinalysis, HIV VL, CD4, PT/INR, hemoglobin A1c, lipid panel, leptin, troponin I, urine hCG (for females of child-bearing potential), , IL-6, apoB, Lp(a), urine albumin:creatinine ratio, anti-drug antibody, and research immunology and inflammation labs.. He/she must be fasting prior to blood draw.

8.1.1.9 WEEK 28 VISIT

At this visit, vital signs, height, weight and BMI, H&P and medication reconciliation will be done, as well as documentation and review of adverse events. The first 6 subjects who had PK samples done at Day 0, Week 2, Week 4, Week 6, Week 16 will also have PK blood samples obtained. The following laboratory tests will be done: CMP, CBC, urinalysis, HIV VL, CD4, PT/INR, lipid panel, leptin, HbA1c, serum hCG (for females of child-bearing potential), Troponin I and T, anti-drug antibody, immunology labs, IL-6, apoB, Lp)a, urine albumin:creatinine ratio. Hs-CRP will also be drawn along with research immunology and inflammation labs. Subjects participating in the FDG-PET/CT will also have GlycA, CEC, and NMR lipoprotein collected. He/she must be fasting prior to blood draw. Transient elastography will be performed to assess for any change seen in hepatic steatosis post-dosing as immediate change within the four-week dosing period would not be expected.

Last, those who had a FDG-PET/CT prior to Day 0 will have a follow-up FDG-PET/CT done at the NIH. Again, this timing allows for potential vascular inflammatory changes to occur over the six month follow up period. Subjects will be provided transportation to and from the NIH if needed.

8.2 ASSAYS

Assays will be performed at one of the following locations:

- NIAID (National Institute of Allergy and Infectious Diseases) Immunopathogenesis section, Building 10
- 2. NHLBI (National Heart, Lung and Blood Institute), Cardiovascular and Pulmonary Branch, Building 10
- 3. Laboratory Corp of America (LabCorp)
- 4. University of Maryland Marlene and Stewart Greenebaum Comprehensive Care Center- Shared Services Core Lab
- 5. Institute of Human Virology Research Lab
 - CMP- comprehensive metabolic panel, serum. This assay will be done through LabCorp. The CMP includes Alanine aminotransferase (ALT/SGPT); albumin:globulin (A:G) ratio; albumin, serum; alkaline phosphatase, serum; aspartate aminotransferase (AST/SGOT); bilirubin, total; BUN; BUN:creatinine ratio; calcium, serum; carbon dioxide, total; chloride, serum; creatinine, serum; eGFR calculation; globulin, total; glucose, serum; potassium, serum; protein, total, serum; sodium, serum.

- CBC- Complete Blood Count with Differential, whole blood. This assay will be done through LabCorp. The CBC includes Hematocrit; hemoglobin; mean corpuscular volume (MCV); mean corpuscular hemoglobin (MCH); mean corpuscular hemoglobin concentration (MCHC); red cell distribution width (RDW); percentage and absolute differential counts; platelet count (RBC); red cell count; white blood cell count (WBC).
- Urinalysis- complete, with microscopic examination. This test will be done by LabCorp. This includes color, appearance, specific gravity, pH, protein, glucose, occult blood, ketones, leukocyte esterase, nitrite, biliriubin, urobilinogen, microscopic examination of urine sediment.
- HIV VL (viral load)- Human immunodeficiency virus 1 (HIV-1), quantitative, real-time PCR (nongraphical), plasma.
- CD4- Helper T-lymphocyte marker CD4, whole blood. This assay will be done through LabCorp. This test includes percentage of CD4⁺; absolute CD4⁺ (helper/inducer); absolute lymphocyte count.
- PT/INR- Prothromibin Time and Partial Thromboplastin Time, whole blood, plasma. This assay will be done through LabCorp. This test includes Activated partial thromboplastin time (aPTT); international normalized ratio (INR); prothrombin time (PT)
- Hemoglobin A1c- whole blood. This assay will be done through LabCorp.
- Lipid Panel- serum (fasting). This assay will be done through LabCorp. This test includes Cholesterol, total; high-density lipoprotein (HDL) cholesterol; low-density lipoprotein (LDL) cholesterol (calculation); triglycerides; very low-density lipoprotein (VLDL) cholesterol (calculation).
- Hepatitis B panel- HBV Evaluation Panel, serum or plasma. This assay will be done through LabCorp. This test includes Hepatitis B core antibody, total; hepatitis B surface antibody, qualitative; hepatitis B surface antigen
- Hepatitis C Ab with reflex RNA- Hepatitis C Virus (HCV) Antibody with reflex to quantitative realtime PCR, serum or plasma. This assay will be done through LabCorp.
- Serum hCG- human chorionic gonadotropin, beta-subunit, qualitative, serum. This assay will be done through LabCorp. A serum hCG will be done for females of child-bearing potential, at the screening visit.
- Urine hCG- human chorionic gonadotropin, beta-subunit, qualitative, urine. This will be a pointof care assay. A urine hCG will be done for females of child-bearing potential before drug dosing, using a point-of-care urine hCG assay.
- Troponin I and T- In conjunction of cardiovascular inflammation measurement, we will also assess myocardial damage using a validated, sensitive cardiac troponin I and T assays (through LabCorp) will be used for all subjects run as batched samples.

- Leptin- serum or plasma (fasting). Used as a marker for lipodystrophy.
- hsCRP (high-sensitivity CRP), serum or plasma. This assay will be done through LabCorp.
- IL-6 (Interleukin- 6), serum or plasma.
- Apo B (apoliprotein B), serum. This assay will be done through LabCorp.
- Lp(a) (Lipoprotein a), serum. This assay will be done through LabCorp.
- Urine albumin /creatinine ratio, random urine. This assay will be done through LabCorp.
- Pharmacokinetic analyses- done for the first 6 subjects receiving CD24Fc.
 For PK analysis, blood samples will be collected prior to drug infusion at weeks 0, 2, 4, 6, 16, 28 before and 2 hours post dosing of CD24Fc as applicable. A +-/10-minute window around each draw point will be allowed. At weeks 6 and 28, a blood sample for PK will also be collected in order to demonstrate a decrease in drug concentration after dosing completion on week 4.

Anti-drug antibody: For ADA analysis, blood samples on day 0 (predosing), week 6, and week 28 visits will be collected. ADA will be measured using a validated assay in a GLP-compliant laboratory that performed these analyses for the phase I and phase IIa CD24Fc studies. Pharmacokinetic parameters will be calculated using actual collection times. In those with pre-existing or induced ADA also completing the PK analysis, effects of ADA on the PK of the drug will be evaluated, although the results from the phase I study demonstrated that a small number of subjects with either pre-existing or induced ADA have similar PK to subjects without ADA.

If ADA is positive, the ADA titration will be done and samples will be saved for neutralizing antibodies when the assay for neutralizing antibodies is available.

When suspected immune related adverse events occur that are potentially related to CD24Fc, the unscheduled samples for ADA analysis will be collected and temporal correlation with a positive binding antibody results will be analyzed and recorded.

All patients with treatment-emergent ADA titer greater than 1:64 should be followed until the ADA titers drop to 1:64 or lower. A titer of 1:64 is equivalent to 5 μ g/ml of reference mouse anti-human CD24 monoclonal antibodies. This threshold is selected based on our phase I data that the patient this titer (the highest in our phase I cohort, and happened to be predosing) experienced neither adverse events nor aberrant CD24Fc PK.

We will follow the recommendation from the White Paper by Shankar²⁷. The treatment emergent ADA response will be defined as ADA is negative in pre-dosing but have positive ADA titers in samples from week 6 or week 28. Persistent ADA response is defined as the ADA titers remain unchanged from Week 6 and Week 28. Transient ADA response is defined the ADA is positive in one time point only.

RNAseq analysis provides an accurate and comprehensive profiling of gene expression. In addition to the immunological approaches, we will use RNAseq data to identify biomarkers for clinical response and PD-markers of drug efficacy. RNA-seq will be used to create a participant profile. RNA sample preparation will have two key steps: (a) RNA will be poly-A selected so that only mRNA is obtained for sequencing and (b) sample from CD24Fc and placebo-treated groups will be multiplexed across lanes and plates to mitigate batch effects from lane and plate bias. Illumina HiSeq sequencer will be used to generate 2x100bp sequencing reads. 3 replicates will be generated per sample, and samples will be multiplexed to obtain ~30M reads per sample; these specifications are common best practices for accurately quantifying mRNA expression.

A local computing cluster will analyze the RNA-seq data using the well-knownSAT-StringTie-Ballgown pipeline ²⁸. This pipeline produces (a) FPKM (fragments per kilobase per million reads), a measure of mRNA abundance, for each gene in a sample and (b) differentially-expressed genes and log-fold change between samples. The performance of this pipeline improves with replicates, so it matches well with this experimental design. Statistical analysis of RNA-seq pipeline outputs will be performed using log transformed intensities and measurements of correlation between the quantified proteome and transcriptome changes in the R software environment. To reduce dimensionality and avoid overfitting, correlations will use only differentially-expressed genes. DAVID ²⁹ will be used to annotate our results with categorical annotation, including Gene Ontology and KEGG pathways for pathway analysis. Enrichment for these categories will be evaluated by Fisher exact test.

• sCD14

Preliminary studies demonstrate that CD24Fc suppresses production of multiple inflammatory cytokines associated with HIV infections. To test the impact of CD24Fc on the systemic inflammatory responses, soluble factors that have been previously demonstrated with negative HIV outcomes (e.g. sCD14) and a larger array of inflammatory factors in the serum (IFNs, TNF etc.) will be quantified. The Luminex platform allows evaluation of over 60 soluble factors and performs bioinformatics analysis to identify factors/patterns of cytokine expression associated with changes in HIV latency.

HIV Reservoirs (Proviral DNA)

Although CD24Fc is not expected to have anti-viral activity, preliminary studies in humanized mice and non-human primate models ³⁰, showed that CD24Fc significantly reduced viral burden in vivo, including proviral burden in the PBL of SIV-infected Macaques rhesus, perhaps by preventing T cell over-activation and its associated exhaustion immunity³⁰. This hypothesis will be tested in ART-treated HIV infected subjects by longitudinal analysis of proviral titers. Established methods for quantification of proviral DNA (droplet digital PCR) will be used as described^{31,32}. Droplet digital PCR will be conducted to quantitate the frequency of cells carrying HIV proviral DNA and cell-associated HIV RNA with single copy sensitivity. The level of replication-competent/infectious HIV in the CD4⁺ T cell compartment will be determined by quantitative coculture assays.

• Inflammatory cytokines

Peripheral blood mononuclear cells will be isolated using Ficoll-Hypaque density gradient technique and used for immunophenotyping. Cells will be washed and stained using appropriate panels of monoclonal antibodies that distinguish cell type (B, T NK, monocyte etc.), cellular

activation states (CD14, CD38, HLA DR, CD25, etc.) and their ability to secrete inflammatory cytokines (IFN, TNF) using intracellular cytokine staining using a 12 color flowcytometry analysis with FlowJo software, at the University of Maryland.

- CD4 and CD8 T cell counts and ratio
 T cell immunophenotyping will be performed as a clinical laboratory test using flow cytometry at the University of Maryland.
- GlycA, plasma. This is a heterogeneous nuclear magnetic resonance signal originating from mobile glycan residues on plasma glycoproteins, used as a novel composite biomarker of systemic inflammation. This assay will be done at the NIH for those subjects completing the optional FDG-PET/CT.
- CEC- cholesterol efflux capacity, plasma. This is an assay assessing HDL function using the macrophage J774 efflux system. This assay will be done at the NIH for those subjects completing the optional FDG-PET/CT.
- NMR lipoproteins, plasma. This is an assay looking at lipoprotein particle size and number using NMR spectroscopy. This assay will be done at the NIH for those subjects completing the optional FDG-PET/CT.
- Endothelin-1, plasma. An ELISA test will be done for subjects at screening and week 28 to look for changes in endothelin-1, which may indicate changes in pulmonary arterial pressure.
- Vascular inflammation, as measured by FDG-PET/CT
 A major challenge in pilot studies attending to study impact of interventions on CVD risk is the requirement of large sample sizes. Recent studies demonstrated that arterial inflammation may be a valuable surrogate marker for CDV risk ³³⁻³⁶. ¹⁸F-fluorodeoxyglucose (FDG) uptake is a sensitive and reliable marker of atherosclerotic inflammation, and this test will be done at the NIH. Measurements will be performed with the ascending aortic root 18F-FDG standardized uptake values (SUVs) as the maximal SUVs using regions of interest. At the same time, blood-pool SUV in the same superior vena cava will also be measured. The maximal SUV will be divided by the blood-pool SUV, yielding a target-to-background ratio (TBR). The average value will be calculated, and the degree of inflammation will be defined based on the TBR value. For our studies, TBR for 12 HIV subjects with LDL levels greater than 125 mg/dL will be imaged before day 0. These subjects will have a repeat FDG PET/CT at week 24 This allows us to compare the mean TBR score using unpaired t tests.

Results of subject's laboratory values and radiologic assessments will be discussed at the completion of study or during the study, in the event of laboratory or imaging abnormalities which require follow-up.

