This study also characterized the single-dose PK of CD24Fc in healthy subjects. The mean plasma concentration of CD24Fc increased proportionally to the doses administered with $t_{\frac{1}{2}}$ of 280.83 to 327.10 hours.

Immunogenicity:

Anti-CD24Fc antibodies were detectable at Day 28 and Day 42 in 1 subject in each of the 5 dose cohorts; however, for the subject in the CD24Fc 120 mg group and the subject in the CD24Fc 240 mg group, anti-CD24Fc antibodies were also detectable pre-dose at levels higher than post-dose levels. Except for those subjects with significant pre-dose anti-CD24Fc antibody levels, all post-dose anti-CD24Fc antibody levels were modest. No deviations in PK were found in any subjects with detectable anti-CD24Fc antibody levels.

Conclusions:

This study showed that the single dose of IV administration of CD24Fc up to 240 mg was safe and well tolerated in healthy subjects. A drug-related SAE of non-sustained ventricular tachycardia was experienced by 1 subject in the CD24Fc 60 mg group. The SAE occurred at a rate comparable with normal populations, was considered mild by the Investigator, and did not lead to discontinuation from the study. There were no clinically meaningful changes from baseline in laboratory parameters, vital signs, ECGs, or physical exams during the study.

For more information, please see section 5.1 of the IB.

CD24FC FOR THE PREVENTION OF ACUTE GRAFT-VERSUS-HOST DISEASE FOLLOWING MYELOABLATIVE ALLOGENEIC HEMATOPOIETIC STEM CELL (PHASE II)

A randomized, placebo-controlled Phase IIa dose escalation trial was conducted to evaluate the addition of CD24Fc to standard of care acute GVHD prophylaxis in cancer patients undergoing allogeneic myeloablative hematopoietic stem cell transplantation (HCT). The trial was designed to define the recommended phase II dose (RP2D) or Maximum Tolerated Dose (MTD) of CD24Fc for acute GVHD prophylaxis. The trial enrolled patients receiving transplants from matched unrelated donors undergoing allogeneic HCT according to institutional practice. This trial exclusively utilized myeloablative conditioning regimens and standard of care prophylaxis comprising tacrolimus and methotrexate since these patients experience the most severe tissue injury and drug will likely have the strongest biological effect in this setting.

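### Section 8.2's ADA duration rules call a first positive at Week 28 transient and leave two post-dose positives with a changed titre unclassified

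*Combined protocol and SAP*

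**What the plan says.** The ADA paragraphs of section 8.2 fix the samples: "For ADA analysis, blood samples on day 0 (predosing), week 6, and week 28 visits will be collected". Section 1.3 (Schedule of Activities) marks the same three visits. Positives are titrated. Section 8.2 names a cited white paper as its source and then writes out three rules:

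- Treatment-emergent: "ADA is negative in pre-dosing but have positive ADA titers in samples from week 6 or week 28".
- Persistent: "Persistent ADA response is defined as the ADA titers remain unchanged from Week 6 and Week 28".
- Transient: "Transient ADA response is defined the ADA is positive in one time point only".

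One further rule uses the treatment-emergent class: "All patients with treatment-emergent ADA titer greater than 1:64 should be followed until the ADA titers drop to 1:64 or lower".

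The visit descriptions do not match this schedule. Section 8.1.1.7 (Week 6) does not list ADA, and section 8.1.1.8 (Week 16) does. ADA presence is a secondary endpoint (sections 3.1.5 and 9.1). Section 9.4.1 leaves further definition of analysis variables to a SAP that is to be finalised before unblinding.

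**The concern.** The transient rule counts positive time points but does not ask for a later negative one. At Week 28, the last scheduled sample, a single positive says nothing about duration, yet the label implies that the response resolved. The persistent rule requires an unchanged titre, not continued presence, so a response that is still there at Week 28 and has grown fails to qualify.

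Both faults lean towards a reassuring description. Someone reading the ADA table would take the transient row to mean antibody that came and went, and would not find every lasting response in the persistent row. With few positives expected, each label carries weight in that table.

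**Working it through.** The plan states no ADA rate or sample-size figure on this point, so there is nothing to reproduce. The check applies the written rules to the possible sample patterns.

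**Step 1: patterns.** Give each of the three samples one of three levels: negative, lower titre, higher titre. That makes 3 × 3 × 3 = 27 patterns. Treatment-emergent requires a negative Day 0 and at least one later positive: 1 × (9 − 1) = 8 patterns. They fall into four pairs:

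| Day 0 | Week 6 | Week 28 | Patterns | Label as written | What was observed |
|---|---|---|---|---|---|
| neg | pos | neg | 2 | transient | resolution |
| neg | pos | pos, same titre | 2 | persistent | still present |
| neg | neg | pos | 2 | transient | duration unknown |
| neg | pos | pos, titre up or down | 2 | none | still present |

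The last two rows are the fault: 4 of 8 patterns. This counts patterns and is not a forecast of how many subjects will show them. All eight remain treatment-emergent, so neither the treatment-emergent count nor the reach of the 1:64 follow-up sentence changes with these labels. If the transient rule is not confined to treatment-emergent cases, a subject positive at Day 0 only is also called transient.

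**Step 2: effect of the Week 16 listing.** If a Week 16 sample is drawn, negative at Week 6 and positive at Weeks 16 and 28 is two positive time points. It is then not transient, but it is not persistent either. A first positive at Week 28 itself is still transient. If the Week 6 sample is missed because section 8.1.1.7 omits it, the persistent rule cannot be applied at all.

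**Step 3: what is known about frequency** (section 2.2.3).

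- Phase I had five cohorts with 6 subjects each on active drug. "Anti-CD24Fc antibodies were detectable at Day 28 and Day 42 in 1 subject in each of the 5 dose cohorts". For the 120 and 240 mg subjects, "anti-CD24Fc antibodies were also detectable pre-dose at levels higher than post-dose levels". If the five subjects were all on active drug and the other three were negative pre-dose (neither is stated), induced ADA was 1 each at 10, 30 and 60 mg: 3/18 = 16.7%, exact 95% limits 3.6% to 41.4%.
- At 240 mg or above: 0/6 in Phase I plus 0/18 in Phase IIa = 0/24. The upper limit is 1 − 0.025^(1/24) = 14.2%. Without the 240 mg subject who was positive pre-dose it is 0/23, upper limit 1 − 0.025^(1/23) = 14.8%.
- Applied to 64/2 = 32 subjects on CD24Fc, the upper limits are 32 × 0.142 = 4.6 and 32 × 0.414 = 13.2 subjects with any induced ADA.

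The two limits differ almost threefold. Neither source matches this trial: Phase I gave single doses, and Phase IIa patients also received tacrolimus and methotrexate. The documents give no share of induced cases that would show either faulty pattern.

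**The case against.** The strongest reply is that nothing planned depends on these labels. The ADA endpoint is presence, timing relative to adverse events, and effect on PK. No section 9.4 analysis uses a duration class, and safety analysis is descriptive. Titres exist for every positive, so a listing would show each pattern whatever its name. This stands, and it is why the point is minor.

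A second reply is that the SAP or the cited white paper may supply better rules. The white paper's text is not in the documents, and no separate SAP is among them. Either could fill the gap for a changed titre. Neither removes the written transient rule; a later document that differed would contradict section 8.2, and the two would need reconciling.

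A third is that titres above 1:64 are followed beyond Week 28. That covers only part of the range, and following until 1:64 or lower does not establish a negative result.

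A reader might also infer that the treatment-emergent definition is wrong because a rise from a positive baseline never counts: five of the 27 patterns show such a rise and none is treatment-emergent. The documents do not support calling this an error. Nothing in them requires a boosted class, and section 8.2 considers pre-existing ADA separately for PK ("In those with pre-existing or induced ADA also completing the PK analysis"). It is a question for the sponsor.

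**Conclusion.** The point holds as a minor fault of wording. On the three scheduled samples, the rules in section 8.2 give a misleading label to a first positive at Week 28, and no duration label to a subject positive at Weeks 6 and 28 with a changed titre. The conclusion rests on a literal reading and on ADA being drawn as section 1.3 and section 8.2 state. A Week 16 sample would narrow the first fault without removing it.

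The effect is confined to the descriptive persistent/transient table. A reader might infer that the immunogenicity endpoint or the LDL result is compromised; neither uses these classes. It would also be tempting to attach a number of affected subjects. Few are expected, but any such number would rest on an assumed share of induced cases and on choosing between 0 of 24 and an inferred 3 of 18.

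**What to change.** Amend section 8.2, and carry the wording into the SAP, before unblinding. For subjects negative pre-dose:

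- *Persistent*: positive at both Week 6 and Week 28, at any titre.
- *Transient*: positive at an earlier post-dose sample and negative at Week 28.
- *Duration not determined*: first positive at the last available sample, or a single positive with the other post-dose sample missing.

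A positive at Day 0 only is pre-existing and gets no duration label. List all titres by visit. Report titre rises in subjects positive pre-dose separately. Check the rules against the white paper that section 8.2 adopts and resolve any difference.

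Reconcile sections 8.1.1.7 and 8.1.1.8 with section 1.3 and the ADA text of section 8.2, because this decides which samples the labels use and whether the Week 6 sample is drawn. If Week 16 sampling stays, add a rule for subjects first positive at that visit.

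Ask the sponsor to state whether a rise from a positive baseline counts as treatment-emergent, and whether the 1:64 follow-up sentence is meant to cover it. No follow-up rule is proposed here.

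The cost is wording only; the labels use samples already in the Schedule of Activities. The downside is that a few subjects may move from transient to an undetermined or less favourable label, and the undetermined group may be a large part of a small total.
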